### 4.6 MISSED DOSES

Subjects should make every effort to take the study drug, belumosudil 200 mg PO BID, at the same scheduled time daily. In the event that the subject misses the planned dose, the following protocol should be followed:

- If  $<$  12 hours of time have elapsed after the scheduled dose, the drug should be taken. The subject should then resume the regular planned daily dosing schedule the following day.
- If  $\geq$  12 hours of time have elapsed after the scheduled dose, the drug should be skipped for that day. The subject should then resume the regular planned dosing schedule the following day.

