## 1.4 CLINICAL EXPERIENCE

### 1.4.1 Clinical Pharmacokinetics

Following a single oral dose of belumosudil 200 mg in the fed state, the mean absolute bioavailability (%F) was 64%. Systemic exposure of belumosudil was increased when administered in the fed state, and in ongoing and planned clinical studies, belumosudil should be taken with food or within 5 minutes of eating.

Across all clinical studies, observed time to reach maximum concentration for belumosudil, belumosudilm1, and belumosudilm2 has ranged from 2-4 hours, and the belumosudil terminal elimination half-life averages ~7 hours following single or multiple dose administration. Exposure of belumosudil (maximum concentration observed and area under concentration curve) in healthy subjects appears to be slightly greater than dose proportional over the 20 to 500 mg once daily (QD) dose range, but less than dose proportional for doses above 500 mg. Little to no accumulation of belumosudil or metabolites, KD025m1 or KD025m2, was observed following multiple dose administration. KD025m1 and KD025m2 exposures are < 5% and ≤ 20%, respectively, of belumosudil exposure.

A [C]-belumosudil human absorption, metabolism, and excretion study confirmed that the majority of radioactivity was recovered in feces (85%), with < 5% recovered in urine. This indicates minimal renal elimination and that the predominant route of clearance of belumosudil and associated metabolites is biliary and/or intestinal.

Cytochrome P450 3A4 (CYP34A) likely plays a predominant role in the metabolism of belumosudil, and in a clinical drug-drug interaction study in healthy volunteers, co-administration with itraconazole (CYP3A4 inhibitor) resulted in a modest 20-25% increase in belumosudil exposure, while co-administration with rifampicin (CYP3A4 inducer) led to a 60-70% reduction in belumosudil exposure.

A delay in absorption and a reduction in belumosudil exposure were observed when belumosudil was co-administered with proton pump inhibitors (PPI) rabeprazole (80-90% decrease) or omeprazole (50-70% decrease), consistent with the finding that increased pH leads to decreased solubility of belumosudil. The clinical relevance of this interaction with PPIs is being evaluated in ongoing studies.

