## 1.6 DOSE RATIONALE

Belumosudil was well-tolerated in Phase 1 studies of healthy volunteers at single doses up to 1000 mg, and with repeat doses up to 500 mg BID for 28 days.

Phase 2 studies of belumosudil have been initiated, enrolling patients with IPF (KD025-207), cGVHD (Study KD025-208 and Study KD025-213) and psoriasis (Study KD025-205, Study KD025-206, and Study KD025-211). More than 600 subjects have been dosed with belumosudil for inflammatory or fibrotic diseases or as healthy volunteers at doses ranging from 20 mg to 1000 mg QD and 500 mg BID.

Preliminary data from phase 2 studies of belumosudil indicate that the dose of 200 mg QD is associated with clinical efficacy and should be well-tolerated in an indication with immune and fibrotic manifestations (e.g., diffuse cutaneous systemic sclerosis [dcSSc]).

This study will evaluate belumosudil at a dose of 200 mg BID in an open study in dcSSc to further evaluate safety and activity.

Also, refer to the [Belumosudil IB](#) for more detailed information.

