### 4.5 TREATMENT COMPLIANCE

Subjects will be given a study drug diary to record the details of each dose of study drug. Diaries will be dispensed/collected on each visit. Compliance with PO dosing will be confirmed using subject diaries, which will be examined at each visit by site staff to determine if dosing is as instructed per protocol and follow-up with the subject accordingly. If the subject skips more than 7 consecutive days of drug dosing (other than those specified in the Dose Modification Guideline for Toxicity), the subject should be discontinued from the study unless approved by the medical monitor and Investigator.

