3.7 Treatment Compliance and Exposure

The relative dose intensity (RDI) will be used to assess the treatment compliance. The RDI is defined as:

$$RDI (\%) = 100 \times ADI (\text{mg/day}) / PDI (\text{mg/day}),$$

where ADI and PDI are the actual dose intensity and planned dose intensity, respectively:

$$PDI (\text{mg/day}) = \text{planned cumulative dose (mg)} / \text{duration of exposure (days)},$$

$$ADI (\text{mg/day}) = \text{actual cumulative dose (mg)} / \text{duration of exposure (days)}.$$

The planned cumulative dose is the planned daily dose amount multiplied by the duration of exposure, while the actual cumulative dose is the sum of actual total daily dose amount over the duration of exposure. The actual total daily dose will need the information of dose modifications (increased and reduced) and dose interruption (held) captured in CRF (Dose Modifications and Interruptions). If a subject does not take any study drug, the actual RDI by definition is zero.

The duration of exposure is defined as:

Duration of exposure (days) = (Date of last dose – Date of first dose) + 1, regardless of unplanned intermittent discontinuations.

One summary table will be generated for treatment exposure and compliance, including: treatment duration (weeks), treatment duration categories (0 to 12 weeks, 12 to 24 weeks, 24 to 28 weeks, 28 to 40 weeks, 40 to 52 weeks), actual cumulative dose, ADI, RDI, and RDI categories (>80%, <=80%; >95%, <=95%).

Another summary table will be generated for dose increased, dose reduced, dose held, and the reasons.

A by patient listing will be generated for the detailed exposure information.

It will be summarized in Safety Population and by group.

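### The missed-dose rule in Protocol 4.6 combines a 12-hour late window with day-based consequences, which does not work for twice-daily dosing on either reading

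*Protocol*

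**What the plan says.** Protocol 4.6 opens with the regimen: "Subjects should make every effort to take the study drug, belumosudil 200 mg PO BID, at the same scheduled time daily". It then gives two branches, triggered by the time since the scheduled dose.

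- Less than 12 hours late: the dose is taken. "The subject should then resume the regular planned daily dosing schedule the following day".
- 12 hours or more late: "the drug should be skipped for that day. The subject should then resume the regular planned dosing schedule the following day".

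Protocol 4.2 and 4.3 confirm that every subject starts on two doses a day. Lower frequencies appear only as toxicity decrements in Table 3 of Protocol 4.12: 200 mg once daily, then every other day.

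Protocol 4.5 makes the rule the standard for compliance review. Diaries are "examined at each visit by site staff to determine if dosing is as instructed per protocol", and staff follow up with the subject accordingly. Discontinuation has a separate trigger, "If the subject skips more than 7 consecutive days of drug dosing", with an exception if the medical monitor and Investigator approve.

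SAP 3.7 measures compliance by relative dose intensity (RDI). The actual daily dose draws on "dose modifications (increased and reduced) and dose interruption (held) captured in CRF (Dose Modifications and Interruptions". Missed tablets are not named there.

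**The concern.** The trigger in 4.6 concerns a single dose, but the consequences are stated for the day. With one dose a day the two agree. With two doses a day they do not, and the text does not say whether the evening tablet is due after a missed morning tablet. The 12-hour cut-off adds a second problem: at 12 hours the next tablet is due, so the window cannot separate a late dose from the next one.

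What is at stake is uniform delivery of the 200 mg twice-daily regimen that the trial is meant to evaluate, avoidance of nearly coincident tablets, and a clear standard for diary review. With 5 to 6 centers and 12 to 15 subjects treated for 52 weeks, it is plausible that sites will read the rule differently.

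**Working it through.** The plan gives no figure to reproduce. The check traces each branch on a schedule.

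**Inputs.** Twice-daily dosing, the 12-hour cut-off and the two branches are from Protocol 4.6. The 08:00/20:00 schedule is an assumption. The day to be skipped is taken as the day of the missed dose.

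**Two readings.** By the day: the skip and the next-day resumption apply to the whole day. By the dose: only the missed tablet is skipped, and the next scheduled tablet is taken as usual.

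**Morning dose noticed at 12 hours or later** (last dose Sunday 20:00; Monday 08:00 missed)

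- By the day: next dose Tuesday 08:00. Gap = 4 h to midnight + 24 h + 8 h = 36 h. Lost: 2 tablets = 400 mg.
- By the dose: next dose Monday 20:00. Gap = 4 h + 20 h = 24 h. Lost: 1 tablet = 200 mg.

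**Morning dose taken h hours late, h below 12**

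- By the day: the schedule resumes on Tuesday, so Monday evening's tablet is displaced. Lost: 1 tablet. The gap from the late tablet to the next is 24 − h.
- By the dose: no tablet is lost. The gap from the late tablet to the evening tablet is 12 − h.

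| Hours late (h) | By the day: gap to next tablet (24 − h) | By the dose: gap to next tablet (12 − h) |
|---|---|---|
| 1 | 23 h | 11 h |
| 6 | 18 h | 6 h |
| 11 | 13 h | 1 h |

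**Evening dose** (Monday 20:00 missed)

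- Noticed at 12 hours or later: next dose Tuesday 08:00, 24 h after Monday 08:00. One tablet is lost on either reading.
- Noticed earlier: the tablet is taken and none is lost. At 11 h late (Tuesday 07:00) it falls 1 h before the 08:00 tablet, again on either reading.

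**RDI, only if missed tablets are counted.** Planned dose over 52 weeks = 364 days × 400 mg = 145,600 mg. One missed morning at 12 hours or later:

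- By the dose: 100 × (1 − 200/145,600) = 99.86%.
- By the day: 100 × (1 − 400/145,600) = 99.73%.

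The two readings differ by about 0.14 percentage points per event (200/145,600).

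**Result.** Reading by the day loses tablets that were due and could have been taken. Reading by the dose permits two tablets an hour or less apart. Neither reading gives a workable twice-daily rule.

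**The case against.** The strongest reply is that no site need read the rule by the day. Its trigger is tied to the scheduled dose. If a missed 08:00 tablet is noticed at 22:00, the 20:00 tablet is itself only 2 hours late, and the first branch says to take it. This stands. The text does not plainly order subjects to drop the evening tablet, and a reader who infers that goes too far. The reply does not rescue the rule, because reading it by the dose leaves the 12-hour window, and with it nearly coincident tablets.

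A reader might also draw four stronger conclusions that the documents do not support.

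- **The rule was carried over from a once-daily protocol.** Its wording would suit one, but neither document states its origin.
- **Efficacy suffers.** Protocol 1.4.1 reports that "the belumosudil terminal elimination half-life averages ~7 hours following single or multiple dose administration", so a 36-hour gap invites a pharmacokinetic argument. The documents give neither an exposure-response relation nor a frequency of missed doses, so no efficacy loss or yearly total can be derived.
- **Doubling is an acute toxicity hazard.** Two tablets together are 400 mg, and Protocol 1.6 states: "Belumosudil was well-tolerated in Phase 1 studies of healthy volunteers at single doses up to 1000 mg". Those were healthy volunteers, but nothing in the documents turns 400 mg into an acute safety finding.
- **Analysis or retention is affected.** The mITT Population needs only one dose, the primary analysis uses that population, and an isolated miss comes nowhere near the rule of more than 7 consecutive skipped days. The stated result of diary review is follow-up with the subject.

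**Conclusion.** The rule is wrong as written for twice-daily dosing, and the point is minor. On the assumed 12-hour spacing, one morning dose noticed at 12 hours or later costs two tablets and a 36-hour gap if the rule is read by the day, against one tablet and 24 hours if only that dose is skipped. Read by the dose, a morning or evening tablet just under 12 hours late can be taken almost together with the next.

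No population, endpoint or planned analysis changes. An RDI effect arises only if missed tablets enter the actual cumulative dose, which SAP 3.7 does not make clear, and it is small per event. The conclusion rests on the 12-hour spacing, which the protocol does not state, and on the absence of any passage in either document that settles which reading applies.

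**What to change.** Reword Protocol 4.6 by schedule:

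- **200 mg twice daily:** take a late dose only within a window shorter than the dosing interval (6 hours is an illustration, for the sponsor to confirm). After that, skip that dose only, take the next scheduled dose at its usual time, on the same day if a morning dose was missed, and do not double.
- **200 mg once daily (reduced dose):** keep the existing 12-hour, next-day wording, which works for one dose a day.
- **200 mg every other day (reduced dose):** resume at the next scheduled dose.

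The cost is a few lines in 4.6 and a memo to sites so that diaries are reviewed against one rule. No data, visits or subjects are added. Protocol 12 sends modifications to the IRB/IEC, so the change can travel with the next amendment.

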#### **4.7 PRODUCT ACCOUNTABILITY**

In accordance with regulatory requirements, study sites must document the amount of investigational product (IP) received from and returned to the sponsor, and the amounts of IP dispensed to study subjects, and the amount returned by study subjects. Product accountability records must be maintained throughout the course of the study.

#### **4.8 CONCOMITANT MEDICATION AND THERAPIES**

All concomitant medications taken during the study and relevant procedures will be recorded on the eCRFs.

Subjects will be counseled to avoid non-prescribed medicines or complementary alternative medicines excluded by the study. All medications a subject receives from the signing of the ICF through the 28-day Follow-up Visit will be documented.

After discontinuation of study drug, any medication used in response to an AE is to be recorded on the appropriate eCRF.

The concomitant medication names will be coded by the sponsor according to the World Health Organization Drug Dictionary and classified by anatomical therapeutic chemical categories

#### **4.9 CYP3A4 INHIBITORS/INDUCERS**

CYP3A4 inhibitors/inducers should be used with caution ([Appendix G](#)).

#### **4.10 DRUGS PROLONGING THE QTc INTERVAL**

Subjects on concomitant medications known to have the potential for QTc prolongation will be excluded ([Appendix H](#)).

#### **4.11 OVERDOSE**

Doses of belumosudil considered to represent an overdose have not been defined. In clinical studies of belumosudil, repeat dosing of 1000 mg QD for 7 days and 500 mg BID for 28 days were generally well tolerated in healthy volunteers. There are no known antidotes to belumosudil, and no specific treatment is recommended in the event of a suspected overdose. The treating Investigator should employ clinical judgment in managing subjects with suspected overdose. Overdose should be reported as an AE.

#### 4.12 DOSE MODIFICATION GUIDELINES

Any clinically significant toxicity will necessitate consideration of either a pause or cessation of therapy. Guidelines for management of treatment-emergent toxicities in subjects receiving belumosudil are outlined in [Table 2](#):

**Table 2 Guidelines for Management of Treatment-emergent Toxicities**

Toxicity	Recommended Action
Grade $\geq 3$ LFTs (AST, ALT, or total bilirubin)	

• Complete the “Treatment-emergent LFT Elevations” eCRF

• Discontinue belumosudil

Other Grade $\geq 3$ clinically significant toxicities considered related to belumosudil	

• Discontinue belumosudil

Grade 2 clinically significant toxicities	

• Consider pause or dose modification of therapy

• Dose interruption for toxicity will be permitted up to 14 days. If toxicity resolves to Grade 1 or below then consider resuming belumosudil at current dose or 1 dose decrement as outlined in Table 3

• If toxicity recurs, hold dose as above then consider resuming belumosudil at 1 dose decrement

• If toxicity does not resolve to Grade 1 or below for 14 days, subjects will be discontinued from treatment

ALT = alanine aminotransaminase; AST = aspartate aminotransaminase; eCRF = electronic case report form; LFT = liver function tests

Dose interruption for toxicity management for 14 days is permitted. Subjects requiring pauses of more than 14 days will be discontinued from the study unless approved by the medical monitor.

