### **9.6.2 Stopping Criteria for Subjects**

Subjects will be discontinued from the study at any time for the following reasons:

1. Grade  $\geq 3$  LFT increase (AST, ALT, or total bilirubin)
2. Grade  $\geq 3$  clinically significant toxicity considered related to belumosudil
3. QTc  $> 500$  ms or AE of *Torsades de pointes*

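### Table 2 ties the non-LFT Grade ≥3 stop to drug-relatedness but not the Grade 2 stop, and the Grade 2 row conflicts with the note beneath the table on trigger, waiver and consequence

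*Protocol*

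**What the plan says.** Protocol section 4.12 opens with a general duty: "Any clinically significant toxicity will necessitate consideration of either a pause or cessation of therapy". Table 2 then gives three rows under a column for recommended actions.

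- **Row 1** covers Grade ≥3 "LFTs (AST, ALT, or total bilirubin") and calls for belumosudil to be discontinued. It has no relatedness condition.
- **Row 2** covers other Grade ≥3 "clinically significant toxicities considered related to belumosudil" and also calls for discontinuation.
- **Row 3** is headed "Grade 2 clinically significant toxicities". Its first action is "Consider pause or dose modification of therapy". It permits an interruption of up to 14 days, with resumption if the event falls to Grade 1 or below, and it closes with "If toxicity does not resolve to Grade 1 or below for 14 days, subjects will be discontinued from treatment".

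The note under the table states a further rule: "Subjects requiring pauses of more than 14 days will be discontinued from the study unless approved by the medical monitor".

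Section 9.6.2 lists three grounds for taking a subject off study: Grade ≥3 LFT increases; Grade ≥3 "clinically significant toxicity considered related to belumosudil"; and QTc above 500 ms or Torsades de pointes. It has no Grade 2 item.

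**The concern.** Two problems are visible on the page.

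The first is relatedness. Row 2 needs the investigator to consider the event drug-related before the stop applies. Row 3 covers a lower grade, has no such condition, and still ends in mandatory wording. Read literally, the milder unrelated event can meet a firmer instruction than the more severe one.

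The second is internal to the Grade 2 provisions. Row 3 and the note under the table both use 14 days, but they attach it to different things and lead to different outcomes.

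What is at stake is consistency between sites in a very small single-arm trial. Two sites could make opposite stopping decisions for the same event and both claim to follow the protocol. Only subjects withdrawn before any study drug are replaced (Protocol 3.8), missing efficacy values are not imputed (SAP 3.1.6), and the main summary is the number and percentage reaching CRISS60 at Week 24 in the mITT population (SAP 3.8.1). A discontinuation decided by interpretation therefore feeds directly into the reported figures.

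**Working it through.** The plan gives no figure to reproduce here. The check is a side-by-side reading, followed by one line of arithmetic.

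**Step 1: which row does each clinically significant event match?**

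| Event | Related | Unrelated |
|---|---|---|
| Grade ≥3 LFT | Row 1: discontinue | Row 1: discontinue |
| Grade ≥3 non-LFT | Row 2: discontinue | No row |
| Grade 2, unresolved for 14 days | Row 3: mandatory wording | Row 3 if read literally: mandatory wording |

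The inversion sits in one comparison: unrelated non-LFT Grade ≥3 against unrelated Grade 2. Section 9.6.2 does not close the gap, because item 2 repeats the related-only limit. Item 3 (QTc/Torsades) has no relatedness condition, so it removes those events from the unmatched cell. What remains falls to three judgement provisions: the opening sentence of 4.12, the investigator's power to withdraw a subject in 3.7, and the reasons in 3.9 that cover an AE requiring permanent discontinuation and investigator decision.

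**Step 2: does the word toxicity settle row 3?** It is not formally defined, and usage points both ways.

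- Towards drug-related: section 9.2 lists it among reactions to an investigational drug.
- Towards any cause: row 2 adds an explicit relatedness phrase, which would be redundant if the word already carried that meaning. The table's title speaks of treatment-emergent toxicities, and SAP 3.9.1 defines treatment-emergent AEs by timing alone. Protocol 9.9 speaks of toxicity grading for laboratory shifts without regard to cause. Row 1 applies whatever the cause.

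A careful site could defend either reading.

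**Step 3: row 3 against the note.**

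| | Row 3, last bullet | Note under Table 2 |
|---|---|---|
| Trigger | Event not down to Grade 1 or below for 14 days | Pause longer than 14 days |
| Waiver | None stated | Medical monitor may approve |
| Consequence | Off treatment | Off study |

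A subject who keeps dosing through a persistent Grade 2 event, which row 3 allows because a pause need only be considered, meets the row but not the note. A subject whose event resolves within 14 days but whose pause runs longer meets the note but not the row. This conflict does not depend on what toxicity means. The treatment/study difference also appears between rows 1 and 2, which stop belumosudil, and 9.6.2, which takes the subject off study for the same events.

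**Step 4: weight of one subject.** Planned enrolment is 12 to 15 (Protocol 3.2, 9.7.2; SAP 3.1.2). With all treated subjects as denominator, one subject is 1/n:

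- 1/15 = 6.7%
- 1/12 = 8.3%

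A smaller denominator, such as only those observed at Week 24, would make each subject weigh more.

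**The case against.** The best defence is that Table 2 is headed as guidelines with recommended actions, and that row 3 should be read as one sequence: consider a pause, interrupt for up to 14 days, resume if resolved, stop if not. On that reading the last bullet simply ends the pause, runs on the same clock as the note, and inherits the medical monitor's discretion. Toxicity would mean a drug reaction, as section 9.2 suggests. Disease progression has its own entry in 3.9, and 9.5.1 exempts laboratory values consistent with the present disease state. Leaving unrelated severe events to the investigator is then a legitimate choice. The trial is also exploratory and descriptive, stopped subjects stay in the mITT population, and the EOT visit collects the CRISS components.

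Much of this is fair. It shows that the relatedness problem is an ambiguity rather than a proven inverted rule. It does not remove the ambiguity, because row 2's explicit qualifier points the other way. Nor does the sequence reading supply the missing waiver, or explain why one sentence ends treatment and the other ends study participation. An EOT visit after an early stop is also not the Week 24 visit, and I find no rule in the SAP for using it as such.

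A reader might infer something stronger: that the table forces discontinuation for Grade 2 events of any cause while worse unrelated events go unaddressed, and that this biases the Week 24 response because those stopped would have more active disease. The documents do not support that:

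- Unrelated Grade ≥3 LFT elevations match row 1, and QTc/Torsades is covered in 9.6.2.
- Sections 3.7, 3.9 and 4.12 provide for other unrelated severe events through judgement.
- Any-cause scope is inferred from a missing phrase attached to an undefined word.
- Nothing gives the expected frequency of persistent unrelated Grade 2 events or shows who would be stopped, so any count of affected subjects and any direction of bias would be assumption.

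**Conclusion.** The point holds in a limited form. Row 3 of Table 2 lacks the relatedness condition that row 2 and 9.6.2 item 2 carry. Taken literally, it therefore gives mandatory stop wording to a persistent unrelated Grade 2 event, while an unrelated non-LFT Grade ≥3 event outside the QTc/Torsades item is left to judgement. Independently of that, row 3 and the note beneath the table disagree on trigger, waiver and consequence.

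The size is 6.7 to 8.3 percentage points on any all-subject percentage for each subject whose discontinuation depends on the reading. This assumes 12 to 15 treated subjects, all in the denominator. The number of such subjects, and the direction of any effect on the response figures, cannot be established from the documents. Because these are stated rules that can send sites to opposite decisions, and not merely missing detail, they should be corrected even in an exploratory trial.

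**What to change.** Reconcile the three rows of Table 2, the note beneath it and section 9.6.2 with one another on four matters:

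1. whether relatedness to belumosudil is a condition in each row, with the meaning of toxicity stated;
2. what the 14 days measures, an unresolved event or a paused dose;
3. whether the medical monitor's approval applies in the row as well as in the note;
4. whether the consequence is discontinuation of treatment or of study participation.

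Which clinical rule applies in each case is for the sponsor's medical team to decide; this review does not propose one.

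The cost is protocol wording in section 4.12 and section 9.6.2, plus a notification to the 5 to 6 sites. No visits or procedures are added.
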